8.2.1 Repeatability Coefficient

8.2.1.1 Repeatability coefficients using observed values

• Computation of the Endpoint

The repeatability coefficient is the value under which the difference between any two repeat measurements of the same measurand acquired under repeatability conditions should fall within 95% probability.

If we assume normality of the repeated measurements, we have:

Repeatability Coefficient = 1.96
$$\times \sqrt{\frac{\sum (m_2 - m_1)^2}{n}}$$

Page 17 of 38

Version Date: 2022-12-16 Version: 2.0

Statistical Analysis Plan – AT01-001

where m_1 and m_2 are the two measurements performed on each of the n subjects.

• Analysis of the Endpoint

Summary tables with the repeatability coefficients for SUVpeak and SUVmax by organ will be produced 2 different ways:

- 1. Within Reader by Reader and Visit: where m₁ and m₂ are the 2 reads for a specific reader and visit.
- 2. Between Visit by Reader: where m₁ is the average of the 2 reads for a specific reader at Visit 1 and m₂ is the average of the 2 reads for the same reader at Visit 2.

8.2.1.2 Repeatability coefficients and within-subject coefficient of variation using log-transformed data

• Computation of the Endpoint

For the following calculations, $d_{ln} = \ln(m_2) - \ln(m_1)$ and m_1 and m_2 are the two measurements performed on each of the n subjects:

The repeatability coefficient is estimated as RC = $(\exp(\pm 1.96\text{SD}(d_{ln}))-1) \times 100$.

The within-subject coefficient of variation is wCV% = $(\exp(SD_{d \ln}/\sqrt{2}))-1) \times 100$.

• Analysis of the Endpoint

A summary table with the 95% repeatability coefficient and within-subject coefficient of variation for SUVpeak and SUVmax by organ will summarize repeatability in 2 different ways:

- 1. Within Reader by Reader and Visit: where m₁ and m₂ are the 2 reads for a specific reader and visit.
- 2. Between Visit by Reader: where m₁ is the average of the 2 reads for a specific reader at Visit 1 and m₂ is the average of the 2 reads for the same reader at Visit 2.

In addition to the above statistics, descriptive statistics of the average of and difference of m_1 and m_2 will be presented.

All of these analyses will be conducted on the image evaluable population for subjects with organs/visits where positive AT-01 uptake is detected by all three expert radiologists.

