| slow IV bolus. | • Change from Baseline in clinical laboratory values at Visits 2 and Safety Follow-up 1 (1-3 days after the second administration of ¹²⁴ I-AT-01). | | | |
| | Change from Baseline in vital signs. | | | |
| | Change from Baseline in ADA. | | | |

Design/Methodology:

This is a multicenter, open-label, single arm study in subjects with AL or ATTR systemic amyloidosis. ¹²⁴I-AT-01 is the only study intervention; neither reference therapy nor placebo will be administered.

| Number of Subjects Planned: | Gender: | Age: |
|-----------------------------|----------------|------------------|
| Approximately 20 | Male or female | ≥18 years of age |

| Protocol Number: AT01-001 | Version: 1.0 | For National Authority |
|-------------------------------------|---------------------|------------------------|
| IND Number: 132282 | EudraCT Number: N/A | Use Only |
| Sponsor: Attralus, Inc | | |
| Investigational Product: 124I-AT-01 | | |

Title of Study: A Multicenter, Open-label, Single-arm, Phase 2 Study to Evaluate Safety and Organ Uptake Quantitation Repeatability of ¹²⁴I-AT-01 using Positron Emission Tomography/X-ray Computed Tomography (PET/CT) in Subjects with Systemic Amyloidosis

Diagnosis and Key Criteria for Eligibility:

Eligible subjects will have:

- Has a history of AL or ATTR systemic amyloidosis with at least one organ with clinically demonstrable amyloid involvement.
- Able to undergo 2 PET/CT scans as part of the study, including ability to lie supine for up to 1 hour.

| | | Treatment Duration: Approximately 6 weeks | |
|---|-------------|---|--|
| Investigational Product, Dose, and Route of Administration: $^{124}\text{I-AT-}01$, 1 mCi $\pm 10\%$ (≤ 2 mg AT-01) via IV infusion or slow IV bolus at 1 mL/5 seconds | Cont N/A | rol, Dose, and Route of Administration: | |

Organ Uptake Quantitation Evaluation:

The repeatability of organ-specific quantitation of radiotracer uptake will be assessed using PET/CT imaging of ¹²⁴I-AT-01 in subjects with AL or ATTR systemic amyloidosis.

The signal to noise ratio (SNR) and contrast to noise ratio (CNR) will be plotted against standardized uptake value (SUV) based metrics. Repeatability will be assessed using Bland-Altman plots. Intraclass correlation coefficient (ICC) and its associated 95% confidence interval will be presented.

Safety Evaluation:

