5.5 Subject Replacement

Subjects that are withdrawn (except for an AE) or are lost to follow-up during the study may be replaced to ensure an appropriate number of subjects complete the study. The decision to replace a subject will be made in agreement between the Sponsor and Investigator. Subjects who do not receive a second dose of ¹²⁴I-AT-01 or have a PET/CT scan following the second dose of ¹²⁴I-AT-01 will be replaced.

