9.3 Sample Size Determination

A formal sample size calculation is not provided for this study. The sample size of up to 20 subjects was estimated based on systematic literature review analysis sets.

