9.5.1 General Considerations

This is an open-label, single arm study. In general, for continuous variables, the mean, standard deviation (SD), median, and range will be presented. Categorical variables will be summarized by frequency counts and percentages.

Subject disposition will be summarized for all subjects who signed the ICF and will include the number of subjects who received study treatment and the number and percentage of subjects who completed or prematurely discontinued the study, classified by reasons for premature discontinuation.

Discontinuations

The reason for study discontinuation and the number of days post-study drug treatment on which the subject discontinued will be summarized.

Protocol Deviations

Protocol deviations will be provided in a listing with reasons for the deviation and the date of occurrence. Any exclusion of subjects from exploratory analysis populations, and how these exclusions impact data analysis, will be addressed in the clinical study report.

Missing Data

There will be no imputation for missing safety or whole blood radioactivity data.

9.5.2 **Primary Endpoint(s)**

The primary objective of this study is to evaluate the repeatability of organ-specific quantitation of radiotracer uptake following PET/CT imaging of AT-01 in subjects with AL or ATTR systemic amyloidosis. The corresponding primary endpoint is:

 Repeatability coefficient (Bland-Altman plots) and intraclass correlation coefficient (ICC) associated with the quantification of radioactivity associated with organ level ¹²⁴I-AT-01 uptake measurements.

The signal to noise ratio (SNR) and contrast to noise ratio (CNR) will be plotted against standardized uptake value (SUV) based metrics. Repeatability will be assessed using Bland-Altman plots. ICC and its associated 95% confidence interval will be presented. Quantitative organ uptake analyzed by an automated method will be summarized. Between-reader agreement in visual determination of AT-01 uptake will be evaluated by Cohen's kappa.

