3.3 Study Design

This is a multicenter, open-label, single arm study in subjects with AL or ATTR systemic amyloidosis. ¹²⁴I-AT-01 is the only study intervention; neither reference therapy nor placebo will be administered.

This study consists of a screening period of up to 30 days; two, one-day treatment periods (Day 1 and Week 6); a safety follow-up 1-3 days after the second administration of 124 I-AT-01, and a final safety follow-up 28 ± 3 days after the second administration of 124 I-AT-01. Thus, the total subject duration is approximately 14 weeks. A study flow chart is provided in appendix 14.1 and a schedule of events is provided in appendix 14.2.

A formal sample size calculation is not provided for this study. The sample size of up to 20 subjects was estimated based on systematic literature review analysis sets.

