8.2.2 Bland-Altman Plots

• Computation of the Endpoint

Document Control No.: TMP-SA-008-01

Each of the n subjects will be represented on the graph by assigning the mean of two measurements as the x-value and the difference between the two measurements as the y-value:

$$\left(\frac{m_1+m_2}{2},m_2-m_1\right)$$

Page 18 of 38

Version Date: 2022-12-16 Version: 2.0

Template Effective Date: 23 Mar 2021

where m_1 is the first measurement and m_2 is the second measurement taken for each of the n subjects. The x-axis will be labeled "Average of the two measurements" and the y-axis will be labeled "Difference between two measurements". A horizontal solid line will be plotted at the mean difference between the values (i.e. $y = \bar{x}$). Horizontal dashed lines will be plotted

at the limits of agreement given by: $= \bar{x} \pm 1.96 \times \sqrt{\frac{\sum ((m_2 - m_1) - \bar{x})^2}{n}}$, where $\bar{x} = \frac{\sum (m_2 - m_1)}{n}$.

The values of all 3 horizontal lines will be displayed on each plot.

• Analysis of the Endpoint

Plots will be produced for SUVpeak and SUVmax by organ for the Image Evaluable Set in 2 different ways:

- 1. Between Reader by Visit: where m_1 is the average of the 2 reads for a specific reader and visit and m_2 is the average of the 2 reads for a different reader for the same visit.
- 2. Between Visit by Reader: where m₁ is the average of the 2 reads for a specific reader at Visit 1 and m₂ is the average of the 2 reads for the same reader at Visit 2.

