8.3 Examination of Subgroups

The repeatability coefficients, Bland-Altman plots, and intraclass correlation coefficients described in section 8.2 will be repeated by amyloid type: (AL versus ATTR).

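### The SAP specifies no confidence interval for the repeatability coefficient, the within-subject CV or the Bland-Altman limits, so no between-visit SUV result has a stated precision

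*SAP*

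**What the plan says.** Protocol 3.0 and 9.5.2 name two parts of the primary endpoint: the RC (with Bland-Altman plots) and the ICC.

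- **RC and wCV.** SAP 8.2.1.1 defines the RC on the observed scale and states: "Summary tables with the repeatability coefficients for SUVpeak and SUVmax by organ will be produced 2 different ways". The two ways are within reader (by reader and visit) and between visits (by reader). SAP 8.2.1.2 defines a log-scale RC and the wCV for the same two comparisons, and adds descriptive statistics of the average and difference of the two measurements. The 95% attached to the RC there is its built-in coverage, not a confidence level. All of 8.2.1 is restricted to organs and visits that all three expert radiologists call positive.
- **Bland-Altman.** SAP 8.2.2 draws the mean difference and two limits: "The values of all 3 horizontal lines will be displayed on each plot". No interval is given for any of the three lines.
- **Where intervals are specified.** Protocol 9.5.2 says "ICC and its associated 95% confidence interval will be presented". SAP 8.2.3 gives the Fisher z formula for it, and SAP 8.2.5 gives a 95% interval for Cohen's kappa. SAP Section 4 mentions confidence intervals only in a rounding rule.
- **Sample size.** Protocol 9.3: "A formal sample size calculation is not provided for this study". SAP 3.3: "The sample size of up to 20 subjects was estimated based on systematic literature review analysis sets". The synopsis has "Approximately 20", and Protocol 5.5 provides that subjects who do not receive a second dose "or have a PET/CT scan following the second dose of ¹²⁴I-AT-01 will be replaced".
- **Subgroups.** Under SAP 8.3 the RC, Bland-Altman and ICC analyses "will be repeated by amyloid type: (AL versus ATTR").

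**The concern.** The study has no hypothesis (Protocol 9.1), no acceptance limit and no precision target. In a pure estimation study the interval tells the reader how far to trust the estimate.

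The gap falls on the central question. The only ICC planned in SAP 8.2.3 is among readers by visit, so its interval describes reader agreement on one visit's scan. Agreement of SUV between Visit 1 and Visit 2 rests on the between-visit RC, wCV and Bland-Altman plots alone. Protocol 2.1 says the study should help determine whether the agent can be used to monitor progression and treatment response. For that use the size of the between-visit variation, and how well it is known, is the key output. A bare RC from a small sample invites over-reading, most of all when tables by organ and by amyloid type are set side by side.

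**Working it through.** The plan has no precision figure to reproduce, because no sample-size calculation is given. What can be computed is the width of the omitted intervals.

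**Inputs.** n = 20 is the planned size. n = 15, 10 and 6 are assumptions: the documents give no expected count per organ or amyloid type. The RC formulas are those of SAP 8.2.1.

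**1. Raw RC.** SAP 8.2.1.1 uses RC = 1.96 × √(Σ(m₂−m₁)²/n), with uncentred squared differences. If the differences are normal with mean zero, Σ(m₂−m₁)²/σ² is chi-square with n df, so the 95% interval is RC × √(n/χ²(0.975, n)) to RC × √(n/χ²(0.025, n)).

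| n | χ²(0.975, n) | χ²(0.025, n) | Lower multiple | Upper multiple |
|---|---|---|---|---|
| 20 | 34.170 | 9.591 | √(20/34.170) = 0.77 | √(20/9.591) = 1.44 |
| 15 (assumed) | 27.488 | 6.262 | 0.74 | 1.55 |
| 10 (assumed) | 20.483 | 3.247 | 0.70 | 1.75 |
| 6 (assumed) | 14.449 | 1.237 | 0.64 | 2.20 |

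A simulation of 200,000 runs each at n = 20, 10 and 5 gave 95.0% coverage.

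**2. Log-scale RC.** SAP 8.2.1.2 uses (exp(±1.96 SD) − 1) × 100, with SD that of the log differences, so the df are n−1 and the interval is formed on SD before back-transforming. Take an illustrative upper RC of +30%, so 1.96 SD = ln 1.30 = 0.2624.

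- n = 20 (19 df, multiples 0.760 and 1.461): exp(0.2624 × 0.760) − 1 = +22%; exp(0.2624 × 1.461) − 1 = +47%.
- n = 10 (9 df, multiples 0.688 and 1.826): exp(0.2624 × 0.688) − 1 = +20%; exp(0.2624 × 1.826) − 1 = +61%.

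**3. Limits of agreement.** The approximate half-width on each limit is t(n−1) × s × √(1/n + 1.96²/(2(n−1))).

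- n = 20: 2.093 × 0.389 s = 0.81 s, which is 42% of 1.96 s.
- n = 10 (assumed): 2.262 × 0.560 s = 1.27 s, which is 65% of 1.96 s.

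**4. Comparing two groups.** For two independent groups of 10 (assumed), the two-sided 5% F limit corresponds to an RC ratio of √F = 1.93 with 10 and 10 df, or 2.01 with 9 and 9 df (ratio of SDs). Smaller ratios could not be told from chance.

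**The case against.** The strongest reply is that the study is labelled exploratory, tests no hypothesis, and already prints what a reader needs. SAP 8.2.1.2 adds descriptive statistics of the averages and differences, and Section 4 defines these to include the number of subjects, mean and SD. From those a reader could derive intervals for the bias and limits, and the RC with n yields its own. This stands in part: n is largely covered in the RC tables, so what is missing is the printed interval, not the underlying information. It does not explain why the ICC and Cohen's kappa receive intervals and the between-visit statistics do not.

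Several stronger readings are tempting, and the documents do not support them:

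- *The primary endpoint has no interval at all.* The RC is one of two named parts; the ICC has one.
- *The report will contain no such intervals.* SAP Section 2 places table and figure specifications in separate documents, which could include them. Only the SAP text can be judged.
- *Differences between AL and ATTR or between organs would be pure noise.* An AL/ATTR ratio of about 2 would be detectable even with 10 per group; only modest differences would not. No formal comparison is planned.
- *The limits of agreement also lose subjects organ by organ.* The all-readers-positive restriction is written in 8.2.1. The 8.2.2 plots use the Image Evaluable Set without it, so the planned split that reduces their n is amyloid type.
- *Twenty is a hard ceiling.* The synopsis says approximately 20, and subjects without a second dose or scan are replaced.

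**Conclusion.** The omission is real and worth correcting: the SAP text specifies no interval for RC, wCV, bias or limits of agreement, and therefore none for any between-visit SUV repeatability statistic. At the planned n = 20, the data would be compatible with a true raw RC from 23% below to 44% above the reported value. In cells of an assumed 10, the range is 30% below to 75% above. These figures assume normal differences and, for the raw RC, no mean shift between measurements. Cell sizes below 20 are illustrative, though the RC restriction to unanimously positive organs can only reduce n, and the amyloid split reduces it again. This is a gap in reporting precision; it does not make the planned point estimates wrong.

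**What to change.** - **SAP 8.2.1.1:** report a 95% CI for the raw RC, RC × √(n/χ²(0.975, n)) to RC × √(n/χ²(0.025, n)), stating the assumptions of normality and no mean shift.
- **SAP 8.2.1.2:** form the same interval with n−1 df for the SD of the log differences, then back-transform its ends to give intervals for the log-scale RC and the wCV.
- **SAP 8.2.2:** add a 95% CI for the mean difference and for each limit, for example limit ± t(n−1) × s × √(1/n + 1.96²/(2(n−1))), and print n on each plot. Say which divisor s uses: the SAP's limits divide by n, which makes the SD smaller by √(19/20) = 0.975 at n = 20 than the usual n−1 form.
- **SAP 8.3:** carry the same intervals into the AL and ATTR displays.

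The cost is a few lines of text and a little programming, with no new data or visits. The reported precision will look less favourable.

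### The log-scale repeatability coefficient and wCV drop any mean visit change while the limits stay centred on zero; separately, the Bland-Altman limits divide by n and are slightly too narrow

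*SAP*

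**What the plan says.** SAP 8.2.1.1 defines the repeatability coefficient (RC) as the value such that "the difference between any two repeat measurements of the same measurand acquired under repeatability conditions should fall within 95% probability". It computes the RC as 1.96 × sqrt(Σ(m2 − m1)² / n). No mean is subtracted.

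SAP 8.2.1.2 sets d_ln = ln(m2) − ln(m1). "The repeatability coefficient is estimated as RC" = (exp(±1.96 SD(d_ln)) − 1) × 100, and the within-subject coefficient of variation (wCV) is (exp(SD(d_ln)/√2) − 1) × 100. The summary table labels the result as a 95% coefficient. In the between-visit table, m1 and m2 are one reader's averages at Visit 1 and Visit 2. The same section adds that "descriptive statistics of the average of and difference of m_1 and m_2 will be presented"; this is on the raw scale, and no mean of d_ln is planned.

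SAP 8.2.2 draws dashed lines "at the limits of agreement given by" the mean difference ± 1.96 × sqrt(Σ(d − mean)² / n), with d = m2 − m1. "The values of all 3 horizontal lines will be displayed on each plot", so the limits are reported as results.

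On numbers of subjects: "The sample size of up to 20 subjects was estimated based on systematic literature review analysis sets" (SAP 3.3), and "The repeatability coefficients, Bland-Altman plots, and intraclass correlation coefficients described in section 8.2 will be repeated by amyloid type" (SAP 8.3).

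**The concern.** The two RCs treat a mean visit change differently, and the SAP does not say why. On the observed scale a systematic change widens the RC. On the log scale it is subtracted and never added back, while the limits remain centred on a ratio of 1. Multiplying every Visit 2 value by a constant leaves the log-scale RC and the wCV exactly as they were. The limit on the side of the shift is then too close to zero, the other is wider than needed, and the pair no longer holds 95% of differences.

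This matters because the log-scale RC is a percentage, the form a reader would naturally use as a threshold for calling a change real. Protocol 2.1 says the study should help decide whether the tracer can be used to follow progression and response to treatment. A threshold that is too small would let ordinary between-visit differences be read as change.

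The Bland-Altman point is independent of any shift. Those limits are centred on an estimated mean, so a sum of squares about that mean should be divided by n − 1. SAP 8.2.6 uses n − 1 for its own SD. The n in 8.2.1.1 is correct, because no mean is estimated there.

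**Working it through.** **Inputs.** The formulas are those of SAP 8.2.1.1, 8.2.1.2 and 8.2.2, with n up to 20 from SAP 3.3. The documents give neither SD(d_ln) nor an expected shift. Both are assumed: SD 0.15 (range 0.10 to 0.25), with mean changes of −5%, −10%, −20% and +10%.

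**Part 1: log-scale RC, between visits.** Take d_ln ~ N(μ, SD²) and k = μ/SD.

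- Coverage of the SAP limits = Φ(1.96 − k) − Φ(−1.96 − k).
- At k = 0 this is 95.0%, so the SAP's figure is reproduced when there is no shift.
- SAP limits at SD 0.15: exp(±0.294) − 1 = −25.5% to +34.2%, whatever μ is.
- True 2.5th and 97.5th percentiles: exp(μ ± 1.96 SD) − 1.
- Root-mean-square (RMS) limits, the 8.2.1.1 rule on the log scale: exp(±1.96 sqrt(SD² + μ²)) − 1.

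Worked case, a 10% fall: μ = ln 0.9 = −0.105, so k = −0.702. The share below the lower limit is Φ(−1.96 + 0.702) = 10.4%, and the share above the upper limit is Φ(−1.96 − 0.702) = 0.4%. Coverage is 89.2%. The RMS is sqrt(0.0225 + 0.0111) = 0.183.

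| Shift (SD 0.15) | SAP coverage | Below / above SAP limits | True 95% interval | RMS limits | RMS coverage |
|---|---|---|---|---|---|
| none | 95.0% | 2.5% / 2.5% | −25.5% to +34.2% | −25.5% to +34.2% | 95.0% |
| 5% fall | 93.7% | 5.3% / 1.1% | −29.2% to +27.5% | −26.7% to +36.4% | 95.0% |
| 10% fall | 89.2% | 10.4% / 0.4% | −32.9% to +20.8% | −30.2% to +43.2% | 95.4% |
| 20% fall | 68.1% | 31.8% / 0.03% | −40.4% to +7.3% | −41.0% to +69.4% | 97.9% |
| 10% rise | 90.3% | 0.5% / 9.3% | −18.0% to +47.6% | −29.4% to +41.7% | 95.3% |

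At a 10% fall, SAP coverage is 81.6% if SD is 0.10 and 92.9% if SD is 0.25.

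wCV at a 10% fall: exp(0.15/√2) − 1 = 11.2% by the SAP, against exp(0.183/√2) − 1 = 13.8% on the RMS basis.

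These figures treat the parameters as known. With parameters estimated from n = 20 (300,000 simulated samples, SD 0.15), average coverage of a new difference is:

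| Fall | SAP limits | RMS limits | Centred on mean d_ln |
|---|---|---|---|
| 0 | 93.5% | 93.6% | 92.9% |
| 5% | 92.1% | 93.6% | 92.9% |
| 10% | 87.4% | 94.0% | 92.9% |
| 20% | 66.4% | 96.8% | 92.9% |

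Sampling error for scale: at n = 20 and SD 0.15, the 95% CI for SD is 0.114 to 0.219, so the lower limit of −25.5% has a CI of about −20% to −35%.

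**Part 2: Bland-Altman limits.** Width relative to the n − 1 version is sqrt((n − 1)/n). Expected coverage of a new difference comes from the t distribution with n − 1 degrees of freedom.

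| n | Too narrow by | Coverage, divisor n | Coverage, divisor n − 1 |
|---|---|---|---|
| 20 | 2.5% | 92.2% | 92.9% |
| 10 | 5.1% | 89.0% | 90.6% |
| 5 | 10.6% | 81.5% | 85.2% |

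With up to 20 subjects split into AL and ATTR, at least one type has 10 or fewer. The n = 5 row is an assumption about a small subgroup.

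**The case against.** **A shift is not predicted.** The definition assumes repeatability conditions, and the design aims at like-for-like scans: doses about ten radioactive half-lives apart (Protocol 4.2.3), the same administration route and the same post-dose scan window at both visits, AL subjects in haematologic response, and anti-amyloid antibodies excluded. This stands as a reason to expect little shift. It does not exclude one: scans are 6 to 8 weeks apart, concomitant drugs are largely unrestricted (Protocol 6.8.1), and concurrent amyloidosis treatment is recorded (Protocol 8.1.1). Absence of shift should be checked, not built into the estimator.

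**A shift would be visible elsewhere.** True: the observed-scale RC includes it, and the raw difference statistics and the Bland-Altman mean line show it. What remains is that the percentage RC and wCV do not reflect it.

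**Sampling error is large.** At n = 20 and SD 0.15, the true lower limit after a 10% fall (−32.9%) lies inside the CI for the SAP limit, as does the one after a 5% fall. Only the 20% case clearly exceeds it. This limits the weight in a single data set; the error is nonetheless systematic.

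**RMS mixes bias with precision.** At a 10% fall it leaves 4.5% below and 0.1% above its limits, and it over-covers at 20%. That is fair, and it is why mean-centred limits are an acceptable alternative.

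**Scope and size.** The visit-shift argument does not apply to the within-reader table, where both reads are of one scan. The n − 1 effect is small beside sampling error: the 95% CI around a limit of agreement at n = 20 is about ±2.093 × sqrt(3/20)/1.96 = ±41% of its distance from the mean. Nor does n − 1 restore 95%, because the 1.96 multiplier and the estimated mean remain.

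**Conclusion.** The concern holds. SAP 8.2.1.1 and 8.2.1.2 handle the mean difference by different rules without explanation, and the log-scale RC meets the 95% definition only when the mean log change is zero.

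The loss is conditional: none without a shift, about one percentage point for a 5% fall, about six for a 10% fall and about 27 for a 20% fall at an assumed SD of 0.15. It is greater if the SD is smaller. These figures assume normal log differences and concern the between-visit table.

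The divisor in 8.2.2 needs no assumption about a shift: the limits are always too narrow relative to n − 1. The effect is small for the whole study and larger in the AL and ATTR plots.

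**What to change.** 1. In 8.2.1.2, replace SD(d_ln) by sqrt(Σ d_ln² / n) in both the RC and the wCV, to match 8.2.1.1. Report the mean d_ln with its 95% CI beside them (half-width 2.093 × 0.15/√20 ≈ 0.07 at n = 20, SD 0.15). State that these symmetric limits are conservative under a large shift and too wide on the side away from it. An acceptable alternative is limits centred on the mean, exp(mean d_ln ± 1.96 SD) − 1, with the wCV labelled as excluding the mean shift.
2. In 8.2.2, divide by n − 1.
3. As a clarification only, say whether the restriction in 8.2.1.2 "for subjects with organs/visits where positive AT-01 uptake is detected by all three expert radiologists" must hold at both visits for a between-visit pair, and whether it also applies to the Bland-Altman plots.

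The cost is two one-line formula changes, one added table row and one sentence, with no new data. Reported repeatability may look slightly worse.
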